## 5.5 Description of Study Process

Study procedures are outlined below. Based on the study team's experience conducting pilot studies, we understand that piloting minimal-risk interventions across sites with varying institutional policies and patient populations must be flexible in order to ensure that the study can quickly adapt to patient needs as we learn more about them over the course of the study. The study activities currently outlined in the protocol therefore may be adapted without the submission of an amendment in cases where these modifications would pose no additional risk to patients, as determined by the overall PI of the study.

### 5.5.1 Instrument Administration

#### Participant Baseline Survey:

- Participants will complete a baseline survey when they begin study interventions (Appendix 14).
- All data from the interview will be stored in RedCap; if paper copies are used, they will be stored in restricted-access locations.
- Estimated time to completion: 45 minutes.

#### Participant Post-Baseline Survey:

- Participants will complete a post-baseline survey approximately three months after the intervention was administered, as close to the 3-month projected assessment date as possible (Appendix 15).
- All data from the interview will be stored in RedCap; if paper copies are used, they will be stored in restricted-access locations.
- Estimated time to completion: 30 minutes.

#### App-Based Surveys:

- Participants will be prompted by the SMART app to complete the survey.
- The surveys will consist of measures of global quality of life, physical health, PRO-CTCAE questions for 10 symptoms, and an additional question designed to query severe symptoms.
- Survey items will not interfere with participants' use of their phone.
- Symptom surveys are administered daily, and the participant cannot take the symptom survey more than once per day. Quality of life surveys will be given over the weekend. Patients can also submit responses less frequently. Once the participant completes the survey it is removed from their action list. Missed surveys do not remain on the patient's action list and can be completed at the next survey timepoint, as applicable.
- Estimated time to completion: 2-3 minutes.
- Participants and their oncology providers will be given summaries of their survey responses throughout the study through HIPAA-compliant secure email. Patients and clinicians may also choose to have their survey responses mailed to them via priority mail or to receive hard copies.

#### Debriefing Interview:

- Study staff will aim to conduct debriefing interviews with the first few participants enrolled at each site and a purposively sample a subset of patients who enroll later (up to 15 total).
- Debriefing interviews will be administered by study staff following participants' completion of the final post-baseline survey.
- Study staff will discuss the debriefing interviews to identify opportunities for protocol improvement.

Health/Treatment Chart Abstraction:

- Study staff will review participants' medical charts to complete the Health/Tx Information form for the time-points of participants' baseline and post-baseline visits.

Health Care Utilization Chart Abstraction:

- Study staff will review participants' medical charts to complete the Health Care Utilization form after participants' post-baseline visit.
- Patients will complete the Medical Care Resource Form to capture all health care utilization during the study, including care outside of affiliated sites that may not be captured in site medical records.

## 5.52 Intervention Administration

### **5.52a Smartphone Apps**

Instructional Session:

- On Day 0, participants will download, install, and run the SMART and Beiwe apps on their personal smartphones, with assistance from study staff as needed. Participants will receive step-by-step instructions and login information for the apps (SMART App Installation Information is included in SMART App Features and Screenshots (Appendix 5); Appendix 12: Beiwe App Installation Guide iOS and/or Appendix 13: Beiwe App Installation Instructions for Android).
- Participants are registered to the SMART App by a study team member that has access to the clinician dashboard and admin site. Study staff will create an account for the participant by using their mobile phone number. When the participant opens the SMART App, they will be required to login using two-step verification. First, participants will be prompted to enter their mobile number. Next, they will have to enter a 4-digit personal validation code that will be automatically sent to their smartphone via SMS. The app does not ask the subject to enter any personal information (name, date of birth, etc.) and cannot be directly linked to their health records.
- Participants will register in the Beiwe App by using a unique User ID and temporary password and then choose a new password. The subject will be assigned a unique 8-character Participant ID which consists of mixture of numbers and letters. The app does not ask the subject to enter any personal information (name, date of birth, phone number, etc.) and cannot be directly linked to their health records.
- Participants will enter their oncology providers' phone numbers for the "Call my Clinician" button and enter study staff's contact number for the "Call Research Assistant" button.
- At the end of the registration process for Beiwe, the participant will click a button to acknowledge that she has reviewed the privacy information with the RA and provide in-app consent.
- The RA will then review how to use the apps and participants will be given a copy of the SMART App Participant Guide (Appendix 5) and the Beiwe App Participant Guide (Appendix 8) and Summary Sheet for Participants (Appendix 3) which describes the apps and provides directions on how to use its features, frequently asked questions, information regarding Beiwe positive affirmation push notifications, as well a review of the data that is collected and privacy measures.

**Symptom Management:**

- Participants will be prompted daily to answer questions about 10 unique symptoms via the SMART App in the Symptom Survey. If a participant is not experiencing any symptoms that day, they can select “not-applicable”. Over the weekend participants will be administered quality of life surveys (the FACT-G7 and PROMIS Physical Function short form 6b).
- If a participant reports one or more low-risk toxicities, the app will present tailored advice on how she can manage each symptom at home. If participants report high-risk toxicities, they will be instructed that they have reported a toxicity that requires further management from their clinical team and are given the instruction to call their clinician. Their clinician’s phone number will be listed within the SMART app so that it is easily accessible for participants’ use. Please refer to Figure 3 for an overview of this process.
- In order to ensure participant safety, the RAs and apps will emphasize to participants that survey results **will not** be reviewed by a clinician in **real-time**. Thus, surveys cannot be used in place of communicating with clinicians to request help. The reminder will also note that if the participant feels unsafe, she should contact the treating clinician directly.
- Participants and their oncology providers will be given a graphical summary of the symptoms participants reported by participants in-between visits. This is dependent on patient adherence –e.g. if a patient is not using the smartphone application and we are unable to receive symptom data, we will not have data to share with patients or their clinicians and no summary sheet will be provided. See Appendix 4: Sample Clinical Summary Sheet for an example of what the summary data will look like. We will not monitor whether clinicians use the summary sheets, since it is difficult to reliably capture what providers read and absorb.

**5.52b Troubleshooting the SMART App**

The intervention’s participant guides outline common troubleshooting issues and how to solve them. Participants will be instructed to call study staff as soon as possible to report if they are having trouble using the app.

**5.52c Fitness Tracker**

All participants will also receive a Fitbit Charge 3 wearable fitness tracker.

**Instructional Session:**

- Following the completion of the Participant Baseline Survey on Day 0, participants will set up their fitness tracker, with assistance from study staff as needed. Participants will learn how to use the fitness tracker; download the Fitbit smartphone app; learn how to synchronize their device to their smartphone; and work with study staff to synchronize their accelerometer data to the research database.
- In addition to the accelerometer, participants will receive the *Fitbit Participant Guide* (Appendix 11), which describes proper wear and care, charging and battery life, troubleshooting instructions, uploading data, and compliance.
- Participants will be encouraged to contact study staff at any time with questions or issues to help ensure proper wear and use of the fitness tracker.

**Tracking Devices:**

- The accelerometer assigned to each participant will be tracked according to the product serial number and assigned unique ID number.
- Participants will be allowed to keep the accelerometer as a token of appreciation for their participation in the study, and to minimize potential transmission of skin infections (e.g. methicillin-resistant *Staphylococcus aureus*) between participants.

#### Monitoring

- If patients are wearing their accelerometer continuously throughout the day and experience a severe drop in steps (e.g.  $\leq 1,000$  steps in a 24-hour period) that is unlikely to be attributable to external factors (e.g., severe snowstorm or rain), study staff will contact the patient to ask if she is experiencing severe symptoms.

### **5.52d Apps and Fitness Tracker Use and Compliance**

Participants will be instructed to avoid adjusting app settings (for Fitbit, SMART, and Beiwe Apps), to ensure data is collected. If the study team does not receive data from the SMART or Beiwe Apps or fitness tracker, study staff will attempt to contact patients to help resolve the issue remotely or during an upcoming clinic/study visit.

### **5.52e Subsequent Enrollment in a Therapeutic Drug Trial**

Participants in this study may enroll in a therapeutic drug trial at any point after signing consent to participate in this study. However, if a patient enrolls in a therapeutic drug trial that requires structured symptom or toxicity reporting we will record this and perform a sensitivity analysis, excluding any patients who participated in a therapeutic trial after enrollment, to determine whether this impacts our findings. Since this is a feasibility and acceptability trial, we do not want to censor participants.

### 5.53 Compensation

If site policies permit, patients will be provided with a gift-card, Clincard or equivalent valued at \$50 after completing the baseline and post-baseline interviews, to thank patients for their time participating in the study and to minimize attrition. Additionally, participants may be reimbursed for significant study-related expenses (e.g., expenses  $> \$25$  directly attributable to the cost of uploading data from the smartphone app over a cellular data plan) if site policies allow.

## **5.6 Adverse Reactions and Management**

### 5.61 Reporting Adverse or Unanticipated Events

Potential adverse events (AE) for this project are expected to be all non-medical in nature. There is a small chance that participants could worsen repetitive use injuries (e.g., carpal tunnel syndrome) while using the smartphone app. Subjects may experience mild anxiety when answering survey questions about emotional issues or questions about coping challenges or difficulties related to discussing the subject matter. The PI will report unanticipated and serious adverse events to the IRB in a timely manner on an ongoing basis. For the purpose of this study a Serious Adverse Event (SAE) is defined as an event that, as a direct result of the study, causes serious harm to the subject (e.g., hospitalization).

### 5.62 Anticipated Reactions & Reaction Management

Should participants become exceedingly upset, disoriented or fatigued or need to attend to matters of personal care during the surveys, study staff will ask the subject if they would like to take a break or reschedule the survey for another time. In the event that participants experience distress while completing surveys, we will follow standard procedures used in our behavioral health intervention studies for counseling and referral. The PI will be notified immediately, and participants will be provided with the pager numbers for both the study PI and a clinician at the primary site, who will evaluate any participants who are distressed for risk of imminent danger and refer them to appropriate services if they are needed.

## **6.1 Primary and Secondary Endpoints**

### **Primary Endpoints**

- 1) Feasibility of the SMART intervention
- 2) Acceptability of the SMART intervention

### **Secondary Endpoints**

- 2) Perceived efficacy
- 3) Additional patient outcomes, including: health-related quality of life, anxiety and depression, symptom burden, and health care utilization
- 4) Agreement between patient and physician estimates of performance status
- 5) Correlation between data collected from the wearable and smartphone accelerometers
- 6) Predictive ability of wearable accelerometer and smartphone data for patient's performance status and clinically significant events

## **6.2. Sample Size**

The primary objective of this study is to assess the feasibility and acceptability rates of the SMART intervention. A convenience sample of 30 patients will be enrolled to the study, with expected accrual of approximately 15 patients each at a maximum of 2 community oncology sites.

## **6.3 Analysis Plan**

Statistical analysis will be descriptive in nature and will assess feasibility, acceptability, and perceived efficacy, as well as estimate outcomes parameters.

**Feasibility:** Feasibility will be defined as ≥50% approach-to-enrollment rate among eligible participants, and 2) ≥50% 3-month adherence rates to the smartphone app and wearable accelerometer (based upon attrition rates from prior trials of PROs). Patients who complete daily surveys ≥4 days per week over the three-month study period will be considered as adherent to the smartphone app. Patients who wear the wearable accelerometer ≥4 days per week over the three-month study period will be considered as adherent to the wearable accelerometer.

**Acceptability:** Acceptability will be defined as ≥60% of participants “agree” or “strongly agree” that they “would recommend the SMART Study to other patients with cancer receiving chemotherapy;” and <30% of participants answering agree or strongly agree to either question: 1) “Participating in this study placed a substantial burden on me” and 2) “I wish I had not agreed to participate in this study.”

**Perceived efficacy:** Perceived efficacy will be measured by qualitative analysis. We will conduct debriefing interviews with approximately 30 participants and their clinicians (evenly distributed among the community oncology sites) to obtain information about the acceptability of the intervention and recommendations for any modifications to improve any aspects of recruitment, enrollment, education, the timing of study assessments, graphical display of information, and the app that could be improved.

Patient outcomes: We will collect baseline and 3-month outcome data from patient interviews and clinician surveys. At each time point clinicians and participants will be asked to rate the participant's ECOG performance status and EuroQoL EQ-5D index; patients will also be asked to rate their symptoms using the PRO-CTCAE. We will also collect health care utilization data (e.g. nursing calls, emergency department visits, hospitalizations, and hospice referrals) from the medical chart and healthcare utilization logs provided by patients. For purposes of estimating outcomes parameters, the distributions of these patient outcomes will be summarized using descriptive statistics such as means, standard deviations, and proportions, and, where appropriate, cumulative incidence functions. Additional demographic information that will be summarized include age, marital status, race/ethnicity, education, household structure, income, employment, health literacy and numeracy, and cancer treatment associated burden. We will abstract information from the medical chart; e.g., comorbid health conditions, prior chemotherapy regimens, and time since diagnosis.

Correlative analyses:

Agreement between patient-oncologist estimates of performance status will be estimated by Cohen's Kappa statistic. We will descriptively summarize correlations between active (e.g. quality of life and symptoms) and passive (e.g. time spent away from home) data collected from the SMART and Beiwe apps and the wearable accelerometer (average daily steps) with clinical outcomes collected at baseline and post-baseline (i.e. performance status, quality of life, and symptoms assessment as obtained from the PRO-CTCAE and CTCAE). In addition to descriptive analyses and estimating correlations between passive smartphone data and clinical outcomes, passive data may contain information that allows for the prediction of future clinically-relevant events, such as visits to the emergency department, urgent clinic encounter, or hospitalization. By testing for changes in activity, mobility, and social patterns over time as measured through smartphone use may be able to identify significant anomalies in patient behavior in the days prior to relapse. In a study in a cohort with schizophrenia, behavioral anomalies detected in the two weeks prior to clinical relapse occurred at a rate 71% higher than anomalies detected on other days. The method is based on a modification of the Hotelling's T test to detect changes in the distribution of previous passively-measured activity. In our proposed study, this method might be used to query patients in real time to detect if an unscheduled clinical event might occur in the near future.

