The overall goals of this study are to test the combination of two smartphone research platforms, the SMART app and the Beiwe app, and a wearable accelerometer for use in NCI Community Oncology Research Program (NCORP) sites to improve cancer patients’ quality of life and symptom management. The SMART Study (Symptom Management and Reporting Toxicities) has a single-arm research design and aims to assess feasibility, acceptability and perceived efficacy of a wearable accelerometer and two smartphone apps in 30 patients receiving chemotherapy to treat recurrent gynecologic cancers. The SMART intervention refers to the combination of both smartphone apps (SMART app and Beiwe app) and the accelerometer (Fitbit). The SMART app is the technology that is actively collecting symptom reporting information from patients (e.g. patients are receiving surveys, recording their symptoms daily, and receiving tailored symptom management materials on their phone in response). The Beiwe app is the technology involved in the passive data collection of participants’ symptoms (GPS and accelerometer data) without their involvement.

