## 2.0 OBJECTIVES

### 2.1 Primary Objectives

To conduct a single-arm study to assess feasibility and acceptability of two smartphone apps and a wearable accelerometer in 30 patients with gynecologic cancers receiving chemotherapy.

- Feasibility will be defined as: 1) ≥50% approach to enroll rate, and 2) ≥50% 3-month adherence rates to both smartphone apps and the wearable accelerometer.
- Acceptability will be defined as: ≥60% of study participants would recommend the intervention to other patients; and <30% of patients rate the study as burdensome or wish they had not participated.

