In collaboration with RMDY, Dana-Farber study staff were able to design a custom “white-label” digital health platform catered specifically to the patient population involved in this research study. The RMDY platform is comprised of three main components: 1) an app where patients can answer surveys (i.e. NCI PRO-CTCAE survey items) and receive symptom management advice tailored to symptom severity, 2) a web-based clinician dashboard where staff track patients’ symptoms and steps, and communicate with patients, and 3) an administrative website where program content can be managed and generated.

Through the SMART app, patients track their symptoms daily through surveys and then receive tailored symptom management advice based on their reported symptoms. Patients can also track their steps, sleep and heart rate, and communicate with their study team directly through the app. The SMART platform also includes a clinician dashboard and admin site where nurses, providers, and other study team members can login to view and manage patients enrolled to the study. The console also allows study staff to monitor the severity and frequency of symptoms patients are reporting throughout the day, view patient steps, collect patient survey response data, send reminders to patients, and assign program content.

The Beiwe app will be used to passively collect information about participants. Passive data collection is essential because mobile health interventions that require significant patient involvement tend to have higher rates of attrition, and patients’ illness may interfere with their ability to report their symptoms. It is essential to develop an intervention that can be utilized to detect patients’ symptoms or anomalies in their behaviors with minimal involvement. Rapid identification and management of symptoms can improve patients’ quality of life and other disease related outcomes. We anticipate the remote monitoring of patient symptoms using both the SMART app and Beiwe app will allow us to better understand cancer patients’ behaviors and relate them to clinically significant patient symptoms and outcomes. The intervention combination may also provide a method for better identifying clinically meaningful anomalies in cancer patients’ behaviors.

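### SMART Study: sections 2.1 and 6.3 define primary feasibility over different components, and the only app-adherence rule in 6.3 cannot score the Beiwe app

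*Combined protocol and SAP*

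**What the plan says.** All references are to Part 2 of the combined protocol and SAP.

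- **Objective (2.1).** One of the two feasibility conditions is "≥50% 3-month adherence rates to both smartphone apps and the wearable accelerometer". The other is an approach-to-enrollment rate of at least 50%.
- **Analysis plan (6.3).** The matching condition is "≥50% 3-month adherence rates to the smartphone app and wearable accelerometer". The app rule is: "Patients who complete daily surveys ≥4 days per week over the three-month study period will be considered as adherent to the smartphone app". A parallel rule of at least 4 days per week covers wear of the accelerometer. There is no third rule.
- **Endpoint (6.1).** The first primary endpoint is "Feasibility of the SMART intervention". Section 1.0 defines that intervention as the SMART app, the Beiwe app and the Fitbit together.
- **Who delivers surveys (5.5.1, App-Based Surveys).** "Participants will be prompted by the SMART app to complete the survey". The symptom-management text in 5.52a agrees.
- **What Beiwe does (5.31, 5.31a).** Beiwe was the existing platform. Its survey functions were switched off, it was retained for passive data, and a new SMART app took over active collection. "The Beiwe app will be used to passively collect information about participants". The participant only has to install it and leave it running.
- **Type of study (5.1, 6.2, 6.3).** Single arm, 30 patients, descriptive, with no hypothesis test.

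**The concern.** The two sections define the same primary endpoint over different components: three in 2.1, two in 6.3. This is more than a singular in place of a plural. Even if the single app in 6.3 is read generously as both apps, the survey-completion rule has nothing to count for an app that sends no surveys.

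An analyst who follows 6.3 could therefore report the adherence part of feasibility as met for a three-part intervention when adherence to one part was never scored. The enrollment condition does not close the gap, because it does not depend on Beiwe use either. Survey completion is also a doubtful stand-in for Beiwe. Section 5.31 itself argues that "mobile health interventions that require significant patient involvement tend to have higher rates of attrition", so on the protocol's own reasoning the two apps may be used at different rates.

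**Working it through.** **Step 1. Sections side by side.**

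| Component | Counted in 2.1 | Counted in 6.3 | Per-patient rule in 6.3 |
|---|---|---|---|
| SMART app | yes | yes | daily surveys on at least 4 days per week |
| Beiwe app | yes | no | none |
| Fitbit | yes | yes | worn on at least 4 days per week |

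**Step 2. Search for a Beiwe rule elsewhere.** Two texts come close. Section 5.31a describes a safeguard meant to have participants log in to Beiwe at least weekly, supported by push notifications. Section 5.52d has staff contact patients when data stop arriving. Both are operational. Neither says which patients count as adherent, and neither is linked to the 50% threshold. The appendices were not supplied, so the search covers the protocol body only.

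**Step 3. Extreme case.** Assume all 30 patients are in the denominator, so the threshold is 0.50 × 30 = 15. Read the 50% per component. Suppose 15/30 are adherent to the SMART app, 15/30 to the Fitbit, and almost nobody keeps Beiwe running. The adherence part of 6.3 is met. Section 2.1 is not met under any reasonable Beiwe measure.

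**Step 4. Illustrative size.** The plan states no power or expected adherence for SMART, so there is no figure to reproduce. All rates below are assumptions: SMART app 60%, Fitbit 70%, components independent, n = 30, each component needing at least 15.

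Let T(p) = P(Bin(30, p) ≥ 15). Then T(0.50) = 0.572, T(0.60) = 0.903 and T(0.70) = 0.994.

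- Under 6.3: T(0.60) × T(0.70) = 0.903 × 0.994 = 0.897, at any Beiwe rate.
- Under 2.1: 0.897 × T(Beiwe rate).

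| Assumed Beiwe adherence | 6.3 | 2.1 | Difference |
|---|---|---|---|
| 50% | 0.897 | 0.513 | 0.384 |
| 60% | 0.897 | 0.810 | 0.087 |
| 70% | 0.897 | 0.891 | 0.006 |

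Other assumed rates give the same pattern. With SMART app and Fitbit both at 60%, 6.3 gives 0.815, and 2.1 gives 0.467, 0.736 and 0.810 at Beiwe 50%, 60% and 70%. With both at 70%, 6.3 gives 0.987, and 2.1 gives 0.565, 0.892 and 0.981.

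**Step 5. Per component or joint.** Neither section says whether 50% applies to each component or to patients adherent to all of them. Under the joint reading of 6.3, with the Step 4 rates and independence, the per-patient rate is 0.60 × 0.70 = 0.42 and the chance of at least 15/30 is 0.24 instead of 0.90. Adding Beiwe at 70% gives 0.42 × 0.70 = 0.294 and a chance of 0.014. Positive correlation between components would raise these joint figures (0.61 and 0.36 in a simulation with latent correlation 0.6). They show only that the choice of reading matters.

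**The case against.** The strongest reply is that this is unfinished editing with little consequence. Section 6.3 also uses a singular app in its perceived-efficacy paragraph where 2.2 has the plural, which suggests carry-over and not a decision to drop Beiwe. A reader might infer that the investigators deliberately excluded Beiwe; the documents do not show that. The study is descriptive, has 30 patients, and ties no stated go/no-go decision to the threshold. Section 5.1 also promises an assessment of missing data, where gaps in Beiwe data could be reported, and the weekly log-in safeguard shows that Beiwe use was considered.

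Much of this stands, and it limits the weight of the point. It does not remove it. Correcting the singular to a plural would still leave no way to score Beiwe, a missing-data summary is not an adherence criterion, and feasibility is one of only two primary endpoints.

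A reader might also infer that 6.3 greatly inflates the chance of declaring feasibility. The documents do not support that. The large differences require Beiwe adherence of about 50% or less, a rate given nowhere. The attrition argument in 5.31 points, if anything, to a passive app holding up better than a survey app. Beiwe could still fail for technical reasons, so that argument does not settle the rate.

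**Conclusion.** The point holds as a conflict between two definitions of a primary endpoint, together with a missing rule for one component. The text comparison needs no assumed rates: as printed, the adherence part of 6.3 does not depend on Beiwe, while 2.1 and the defined intervention include it.

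The numerical effect is unknown. The extreme case in Step 3 rests on 30 patients in the denominator, the per-component reading, and some Beiwe measure that near-universal non-use would fail. In the Step 4 illustration the difference is below 0.10 once Beiwe adherence is 60% or more and negligible at 70%. It becomes material near 50%. Those statements rest on the per-component reading, independence and the assumed rates. What is affected is a descriptive threshold, not an error rate. The plan should be corrected, but the defect does not invalidate the study.

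**What to change.** Reconcile 2.1 and 6.3 before adherence data are examined, in one of two ways.

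- **A. Score all three components.** Apply the 50% criterion in 6.3 to the SMART app, Beiwe and the Fitbit, and report all three rates. The investigators choose and justify the Beiwe measure from information already available, for example days per week with passive data received, or weekly log-in. Data receipt can fail for technical reasons, so the justification should say why the chosen measure reflects adherence.
- **B. Narrow the claim.** Limit 2.1 and the feasibility conclusion to the SMART app and Fitbit, and report receipt of Beiwe data descriptively.

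In either case, state whether 50% applies to each component or to patients adherent to all.

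The cost is protocol wording. No visits or data collection are added, since Table 2 in section 5.4 already schedules passive app data from Visit 0 to Visit 90. Under A, feasibility may be somewhat harder to declare, by an amount that depends on the unknown Beiwe rate. Under B, the primary conclusion no longer covers the full intervention as section 1.0 defines it.

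### SMART's 60% acceptability criterion is defined on recommending the intervention but scored on recommending the study, a broader object, and no scored acceptability item is specific to the intervention

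*Combined protocol and SAP*

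**What the plan says.** All references are to Part 2 of the combined protocol and SAP.

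- Section 2.1 (Primary Objectives) defines acceptability by two limbs. The first is "≥60% of study participants would recommend the intervention to other patients". The second is "<30% of patients rate the study as burdensome or wish they had not participated". So 2.1 names the intervention in the first limb and the study in the second.
- Section 6.1 lists as a primary endpoint: "Acceptability of the SMART intervention".
- Section 6.3 (Analysis Plan) gives the scoring. The first limb is met if at least 60% agree or strongly agree that they "would recommend the SMART Study to other patients with cancer receiving chemotherapy". The second limb uses two items, one being "Participating in this study placed a substantial burden on me" and the other asking about regret at having agreed to take part. Both are worded about the study.
- Section 1.0 keeps the two terms apart. The intervention is the pair of smartphone apps together with the Fitbit. The study is described as research: "The SMART Study (Symptom Management and Reporting Toxicities) has a single-arm research design".

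**The concern.** The objective and the primary endpoint are about the intervention, but the item that decides the 60% limb is about the study. A participant in the study also completes a baseline survey of about 45 minutes and a post-baseline survey of about 30 minutes (5.5.1). She may receive $50 where site policy allows (5.53) and keeps the Fitbit afterwards (5.52c). She could value the study and find the apps of little use, or like the apps and find the surveys tiresome. Either view would separate her answer to the item from the answer 2.1 asks for.

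At stake is what a met criterion may be said to show. Acceptability is one of two primary endpoints and is declared by fixed cut-offs. As written, it could be declared met or not met without any scored acceptability answer about the apps or the Fitbit themselves.

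**Working it through.** **Comparing the sections.** For the recommendation limb, the object is the intervention in 2.1, the intervention in 6.1 (as the endpoint), and the study in 6.3. For the burden and regret limb, the object is the study in both 2.1 and 6.3, so that limb is consistent. The threshold is 60% in both 2.1 and 6.3. The mismatch therefore lies only in what patients are asked to recommend.

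**Whether the terms could be synonyms.** Section 1.0 defines them separately, and 2.1 uses both within one definition, one per limb. A reader cannot safely treat them as interchangeable.

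**Inputs for the arithmetic.** n = 30 (6.2); thresholds of at least 60% and under 30% (2.1 and 6.3). The plan gives no error rate, power or precision for SMART, and 5.1 rules out formal hypothesis testing, so there is no plan figure to reproduce. I assume all 30 patients answer; with fewer, the pass mark falls and the interval widens.

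**Pass marks.** 0.60 × 30 = 18, so the first limb needs at least 18 of 30; 17/30 = 56.7% fails. 0.30 × 30 = 9, and the inequality is strict, so the second limb allows at most 8 of 30 (26.7%). One patient is worth 1/30 = 3.3 points.

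**Precision at the pass mark.** Exact (Clopper-Pearson) 95% interval for x = 18, n = 30:
- lower limit = 2.5% quantile of Beta(x, n − x + 1) = Beta(18, 13) = 0.406
- upper limit = 97.5% quantile of Beta(x + 1, n − x) = Beta(19, 12) = 0.773

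**Sensitivity of the first limb.** P(X ≥ 18) = Σ from k = 18 to 30 of C(30, k) p^k (1 − p)^(30 − k), where p is the true proportion who would agree:

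| p | P(X ≥ 18) |
|---|---|
| 0.50 | 0.18 |
| 0.55 | 0.36 |
| 0.60 | 0.58 |
| 0.65 | 0.78 |
| 0.70 | 0.92 |

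These values of p are assumptions. Take a true rate of 60% for recommending the intervention. If the study item ran 5 points higher, the chance of meeting the limb would go from 0.58 to 0.78; 5 points lower, to 0.36. At 10 points the figures are 0.92 and 0.18. The documents give neither the size nor the direction of any such gap. The table shows only that a gap of a few points would matter.

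**The case against.** The strongest reply is that the item is a reasonable proxy. SMART has a single arm and every participant receives both apps and the Fitbit. Three months of app and device use probably dominate what a patient means by the study. The threshold is the same in both sections, and 6.3 reads naturally as the working form of 2.1. The analysis is descriptive. The recommendation limb cannot produce a pass alone, because the burden and regret limb must also be met. Evidence about the intervention is also gathered elsewhere: adherence to app and Fitbit under feasibility, and debriefing interviews that ask about the intervention's acceptability.

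Most of this stands, and it limits the point. A reader might infer that the criterion is measured on something unrelated to the intervention; the overlap rules that out. A reader might also infer that the payment and the free device inflate the result. The documents do not support that: payment depends on site policy, the Fitbit is itself part of the intervention (only keeping it is a study extra), and survey burden could pull the other way. An assumed 15-point gap in favour of the study would move the chance of passing from 36% to 92% (55% against 70%) or from 18% to 78% (50% against 65%). Those pairs are hypothetical, run in one direction only and assume 30 responses, so they are not an expected bias. Nor do the documents say what community practice would offer outside the study.

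The reply does not remove the mismatch itself. A proxy for a primary criterion should be stated and justified, and 6.3 does neither. Adherence is not willingness to recommend. The debriefing interviews are qualitative, involve a purposive subset under 5.23, and are filed in 6.3 under perceived efficacy, so they do not score the criterion. Appendix 15, the post-baseline interview, is listed but not reproduced; it may contain items on the apps or Fitbit, but 6.3 scores none of them for acceptability.

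**Conclusion.** The point holds as an inconsistency in how a primary endpoint is measured. Sections 2.1 and 6.1 ask about the intervention. Section 6.3 scores a broader, overlapping object, and its other two acceptability items are also about the study. The met or not-met conclusion may therefore differ from the one 2.1 intends, in either direction. The size of the difference cannot be derived from the documents. With a pass mark of 18 of 30 and an exact interval of 40.6% to 77.3% there, a gap of 5 to 10 points could change the result.

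It would go too far to say that the result is biased upward, or that the study can show nothing about the intervention's acceptability. The conclusion rests on the item as quoted in 6.3 being the one actually put to patients, and the arithmetic rests on 30 responses.

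**What to change.** Add to the 3-month post-baseline survey one item asking whether the patient would recommend the intervention, meaning the apps and Fitbit used together, and score the 60% criterion on it in 6.3. Add separate items on the apps and on the Fitbit as descriptive support, since a patient may like one and not the other and Beiwe runs largely unseen in the background. Keep the present study-level item as a descriptive measure. Leave the burden and regret limb unchanged.

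The cost is one to a few extra questions and a line in 6.3. Patients already surveyed would have only the study item, and their answers should be reported separately.

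If data collection is complete, reconcile 2.1, 6.1 and 6.3, and report the result as willingness to recommend the study, not as acceptability of the intervention.
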